7.4 Baseline Data Collection

The Ontario Renal Reporting System (ORRS) and British Columbia's PROMISE databases will be used to obtain demographic information on all participants enrolled in the study. The Ontario Renal Network has already mandated provincial data collection regarding symptoms/adverse events related to vaccination and COVID-19 infection confirmed by SARS-CoV-2 RT-PCR in hemodialysis and peritoneal dialysis patients. Specifically the following variables will be collected in all participants: age, sex, prior COVID-19 (NP Swab), vascular access, cause of kidney disease, current immunosuppressive medications (defined as taking any of the following: antimetabolite agent, calcineurin inhibitor, cytotoxic medications, rituximab in prior 6 months, tumor necrosis factor alpha monoclonal antibodies, or glucocorticoids greater than prednisone 5 mg daily), autoimmune disease, diabetes mellitus, cancer, coronary artery disease, congestive heart failure, chronic obstructive lung disease, hypertension, obesity, hepatitis B non-responder status (defined as <10mIU/mL), and ABO blood type. In non-dialysis patients serum creatinine and proteinuria will be recorded.

8 ASSESSMENT OF SAFETY

The safety of research participants is foremost and should always be considered throughout the conduct of research.

8.1 Definitions

8.1.1 Adverse Events

An adverse event (AE) means any untoward medical occurrence in a patient or clinical investigation participant administered a pharmaceutical product and which does not necessarily have to have a causal relationship with this treatment, and includes an adverse drug reaction (ADR). An AE can therefore be any unfavorable and unintended sign (including an abnormal laboratory finding, for example), symptom, or disease temporally associated with the use of a medicinal product, whether or not considered related to the medicinal product.

8.1.2 Serious Adverse Events

A serious adverse event (SAE) or reaction is any untoward occurrence that at any dose: Results in death, is life-threatening, requires inpatient hospitalization or prolongation of existing hospitalization, results in persistent or significant disability/incapacity, is a congenital abnormality or a birth defect. The term "life-threatening" in the definition of "serious" refers to an event in which the participant was at risk of death at the time of the event; it does not refer to an event which hypothetically might have caused death if it were more severe.

8.1.3 Unexpected Adverse Event

An unexpected adverse event is any AE that is not identified in nature, severity or frequency in the current Investigator's Brochure or Product Monograph.

8.1.4 Unexpected Adverse Drug Reaction (ADR)

An ADR is an adverse reaction, the severity of which is not consistent with the applicable Investigator's Brochure or Product Monograph. All noxious and unintended responses to a medicinal product related to any dose should be considered an ADR. The phrase "responses to a medicinal product" means that a causal relationship between a medicinal product and an adverse event is at least a reasonable possibility, i.e., the relationship cannot be ruled out. The expression "causal relationship" is meant to convey that in general there are facts, evidence or arguments to suggest a reasonable causal relationship. All serious and unexpected ADRs will have expedited reporting to regulatory agencies following ICH-GCP and local regulatory requirements.

8.2 Assessment of an Adverse Event

8.2.1 Relationship (Causality/Relatedness)

The causality assessment is the determination, according to the investigator's clinical judgment, of the existence of a reasonable possibility that the study drug (IP) caused or contributed to an adverse event. If the investigator or delegated sub-investigator is unsure about whether or not the study drug caused or is related to the event, then the event will be handled as "related" to the study drug for reporting purposes of the trial. If the causality assessment is

"unknown but not related" to the study drug, this should be clearly documented in the source documents.

8.2.2 Expectedness

Events are classified as unforeseen or unexpected if the nature, severity or frequency is not consistent with the risk information set out in the Product Monograph (PM) or label.

8.2.3 Seriousness

Events are classified as serious if associated with effects threatening the life or physiological functions of a participant.

8.2.4 Severity

The term "severe" is often used to describe the intensity (severity) of a specific event (e.g. mild, moderate, or severe myocardial infarction); the event itself, however, may be of relatively minor medical significance (such as severe headache). This is not the same as "serious," which is based on participant/event outcome or action criteria usually associated with events that pose a threat to a participant's life or functioning. The terms "serious" and "severe" are not synonymous. Seriousness (not severity) serves as a guide for defining regulatory reporting obligations.

8.3 Adverse Event Recording

Investigations into potential adverse events should be done during each contact with a participant. Investigations may be done through specific questioning and, as appropriate, by examination. Information on all adverse events should be recorded promptly in the source document, and assessed by an investigator in a timely manner allowing sufficient time to meet required reporting timelines for SAEs and SUADRs if needed. Adverse event CRFs should be completed using source documents by a delegated research team member in a timely manner/within 15 days of site awareness. All clearly related signs, symptoms, and abnormal diagnostic procedures should be recorded in the source document, though should be grouped under one diagnosis.

The following are not considered AEs and therefore do not require recording: Pre-existing diseases or conditions identified and recorded at screening/baseline unless, at the discretion of the investigator, the disease or condition worsens in severity or frequency, at the discretion of the investigator; events considered likely manifestations of the underlying disease or that commonly occur in the study population independent of IP exposure, and elective medical or surgical procedures.

8.4 Reporting of SAEs and Unanticipated Events

8.4.1 Investigator reporting: Notifying the REB:

Serious adverse events and unanticipated events should be recorded and reported to the REB in accordance with local reporting requirements and timelines.

8.4.2 Investigator reporting: Notifying the Sponsor

The investigator is responsible for reporting serious adverse events and serious and unexpected adverse drug reactions (SUADRs) to the sponsor in accordance with applicable

regulations and reporting requirements and timelines. Events that are assessed to be serious and unexpected and related or cannot be ruled out as related to the investigational product are considered SUADRs. Reporting for SUADRs should include a description of the event in sufficient detail to allow for a complete medical assessment of the case and independent determination of possible causality. The minimum information required includes at least one identifiable participant, one identifiable reporter, one serious reaction, and one suspect product.

Additionally, a Suspect Adverse Reaction Report – CIOMS I Form (see appendix B) must be completed by the investigator and forwarded to the Sponsor within 24 hours of site awareness. Information on other possible causes of the event, such as concomitant medications and illnesses should also be provided as soon as is made available.

8.4.3 Sponsor Reporting of SUADRs: Notifying Health Canada

The regulatory sponsor is responsible for reporting SUADRs to regulatory authorities in accordance with local expedited reporting requirements and timelines. In addition, the Sponsor will complete the ADR Expedited Reporting Summary Form and submit this form in conjunction with the completed CIOMS Form to the appropriate Health Canada directorate.

8.4.4 Sponsor Reporting of SUADRs: Notifying Sites

The regulatory sponsor is responsible for distributing blinded expedited reports of SUADRs to each investigator for submission to local Ethics Committees within 15 days of sponsor awareness.

8.4.5 Events of Special Interest

Events of Special Interest in relation to COVID-19 are derived from the Public Health Ontario Report of Adverse Event Following Immunization (AEFI): Vaccine-associated enhanced disease, acute respiratory distress syndrome, acute cardiovascular injury, coagulation disorder, acute kidney injury, acute liver injury, anosmia and / or ageusia, chilblain-like lesions, single organ cutaneous vasculitis, erythema multiforme.

8.5 Type and Duration of Follow-up for Adverse Events

AEs occurring as of the first administered dose of the investigational product and 30-days after the last administered dose, will be collected. AEs recorded during this period will be followed through to resolution, or until the event is assessed as chronic or stable.

8.6 Reporting and Entry Timelines

Study investigators will report SAEs to the sponsor within the following timelines: All deaths and immediately life-threatening events, whether related or unrelated, will be recorded and reported to the sponsor within 24 hours of site awareness. Serious adverse events other than death and immediately life-threatening events, regardless of relationship, will be reported to the sponsor within 72 hours of site awareness. Adverse event information will be entered into the CRF in a timely manner and no later than 15 days from the time the investigator becomes aware of the event. Serious adverse event information will be entered into the CRF in a timely manner/within 72 hours from the time the investigator becomes aware of the event.

8.7 Evaluation of Adverse Events and Safety Questionnaires

Local and systemic AE will be evaluated within 48 hours to 14 days and 1 month post third dose. Local adverse events include pain at the injection site, redness, and swelling. Systemic adverse events include fever, fatigue, headache, chills, vomiting, diarrhea, new or worsened muscle pain, and new or worsened joint pain. Serious adverse events (SAE) will be recorded and investigated and questions will be adapted from the report of Adverse Event Following Immunization (AEFI) from Public Health Ontario, including local reactions at the injection site, symptoms (fever, chills, fatigue, nausea/vomiting, diarrhea, muscle pain, joint pains and other adverse events). Participants will be advised that acetaminophen may reduce vaccine side-effects but will not actively be counselled to medicate, but usage will be recorded. Due to kidney disease, anti-inflammatory medication will be discouraged. A recent study of heterologous prime-boost found increased adverse events with heterologous vaccination but no hospitalizations were recorded, and most adverse events occurred within 48 hours of vaccination.²⁰

In Ontario, all chronic dialysis patients are currently being tracked for serious adverse events using the COVID-19 vaccine tracker although this had not detected any serious adverse events to date. This customized Excel spreadsheet is pre-populated by the Ontario Renal Network (ORN) and completed by renal programs monthly (submitted securely via Tumbleweed systems). Adverse events related to vaccination are also tracked in PROMIS (BC) which has detailed clinical records on their patients. Coordinators will conduct a questionnaire to inquire about local and systemic symptoms related to the vaccine. Other rare adverse events will be captured using detailed descriptions. Questionnaires will be conducted 48 hours -14 days, and 1 month after the booster vaccination dose. Individuals participating in the pilot study have had side effects after the first two doses of vaccine recorded. SAEs are defined using the Health Canada definition as

those resulting in hospitalization admission or prolongation of existing hospitalization, resulting in persistent or significant disability or incapacity, is life-threatening, or resulting in death and definitely or probably associated with vaccination in the opinion of their nephrologist. The provincial data collection includes reasons for vaccine hesitancy or refusal which could inform education for specific groups. In addition, renal programs in Ontario are currently tracking all infections, including the 3 reported variants (B117, B1351, P1, and others).

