4 STUDY DESIGN

4.1 General Design

The BOOST-KIDNEY study is a prospective, investigator and participant blinded randomized four parallel arm controlled study for CKD stage 3b-5 patients to evaluate the effect of a booster dose of vaccine on immunogenicity among those who did not respond defined as not reaching convalescent serum levels of Anti-RBD, or who exhibit declining antibody titers below the convalescent serum level of Anti-RBD. Enrolment will prioritize patients on dialysis but inclusion criteria will also include non-dialysis CKD stage 3b-5. Patients who are already participating in the study “Determining the Safety and Efficacy of COVID-19 Vaccination in the Chronic Kidney Disease Population” (CTO Protocol Number 3604) and have been found to have poor humoral response to COVID-19 vaccination will prioritize for recruitment. However, if a booster dose of COVID-19 vaccine is approved for the study population during the study period, patients will be eligible without serologic evaluation.

Patients will be randomized to mRNA-1273 SARS-CoV-2 Vaccine (*SPIKEVAX®/Moderna*), or BNT162b2 mRNA Covid-19 Vaccine (*COMIRNATY®/Pfizer-BioNTech*) administered by a trained vaccine administrator. Information on prior vaccines received will be recorded, and patients may have received either mRNA-1273 SARS-CoV-2 Vaccine (*SPIKEVAX®/Moderna*), or BNT162b2 mRNA Covid-19 Vaccine (*COMIRNATY®/Pfizer-BioNTech*) for their initial two doses of vaccine. Patients will be stratified by their initial vaccine type (BNT162b2 or mRNA-1273) prior to randomization, which will result in four study groups as shown in Figure 2.

A placebo arm is not included in this study as it was not felt to be ethically justified, but comparison will be made to participants not receiving a booster vaccine enrolled in CTO Protocol Number 3604 who choose not to participate. Similarly a primary outcome of COVID-19 infection

or hospitalizations was not chosen given the low incidence of COVID-19 infections in Canada due to high vaccination rates in the country.

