The third dose of vaccine will be administered between 2 months to 12 months following second dose of vaccine to allow a reasonable window for eligibility, and to allow for the appropriate screening of study participants with suboptimal initial humoral serologic response for this study. Vaccine will be dispensed by the central pharmacies through concealed allocation prior to planned administration of the study intervention. The vaccine will be administered by an individual who

has been trained in COVID-19 vaccine administration. The individual administering the vaccine will not be blinded to the vaccine type. Vaccine receipt will be entered in the COVAX database, and receipt of a booster vaccine dose will be recorded in the Ontario Renal Network COVID-19 vaccine tracker after unblinding following reporting of the adverse events at 30 days.

Participants will be provided with documentation indicating that they have received a third booster dose and the date that this was received after unblinding following the completion of adverse event following immunization. As with standard vaccine administration, participants will sign additional informed consent to receive the vaccine and confirm that they do not have allergies to the components of either vaccine type. Participants will be monitored for 15 minutes following vaccine administration prior to being allowed to return home. For in-centre hemodialysis participants, the vaccine administration will occur during maintenance hemodialysis.

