10 STATISTICAL CONSIDERATIONS

10.1 Study Hypotheses

Based on evidence from the transplant population, we hypothesize that patients who did not initially attain an initial robust immune response to two dose COVID-19 vaccination, a substantial proportion may attain improved humoral and cellular immunity against COVID-19 following a third vaccine booster with acceptable tolerability. We hypothesize that heterologous vaccination (e.g. a different vaccine from the first two doses) for the third dose may result in increased serologic response.

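### No solicited symptom is recorded before the booster, so for six of the eight systemic items the split between vaccine reaction and background rests on unanchored judgement

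*Combined protocol and SAP*

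**What the plan says.** - **Timing.** Section 8.7: "Local and systemic AE will be evaluated within 48 hours to 14 days and 1 month post third dose". Table 1 and Appendix A agree. The questionnaire is marked at 48 hours to 14 days and at 1 month, and not at enrolment, before the booster or at administration.
- **Collection window.** Section 8.5: "AEs occurring as of the first administered dose of the investigational product and 30-days after the last administered dose, will be collected". Collection therefore begins with the dose.
- **Items.** Section 8.7: "Systemic adverse events include fever, fatigue, headache, chills, vomiting, diarrhea, new or worsened muscle pain", followed by joint pain with the same qualifier as muscle pain. Fever, fatigue, headache, chills, vomiting and diarrhea carry no such qualifier. The section also says that coordinators ask about symptoms linked to the vaccine.
- **Baseline.** Section 7.4: "Specifically the following variables will be collected in all participants: age, sex, prior COVID-19 (NP Swab), vascular access". The list goes on to comorbidities, medications and similar variables. None of the solicited symptoms is on it.
- **General filter.** Section 8.3 does not count as adverse events (a) conditions already noted at screening or baseline, unless they worsen, and (b) events that are likely due to the underlying disease or are common in this population whatever the product. It does not say whether these rules govern the questionnaire items.
- **Controls.** Section 4.1: "A placebo arm is not included in this study as it was not felt to be ethically justified". Its substitute is a non-randomised contrast with unboosted patients from the companion cohort (CTO 3604) who decline this trial. No symptom questionnaire is described for that group.
- **Use.** Secondary objective 4 evaluates adverse events related to the third dose. Section 10.1 hypothesises improved immunity "following a third vaccine booster with acceptable tolerability".

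**The concern.** Fatigue, headache and chills can occur in dialysis and advanced CKD patients without any vaccine. Section 6.1.3 adds: "For in-centre hemodialysis participants, the vaccine administration will occur during maintenance hemodialysis". A participant asked up to 14 days later whether a symptom was due to the injection has no record of their state beforehand, and neither has the coordinator.

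Two results are at stake. The first is each vaccine's absolute reactogenicity, on which the tolerability statement in 10.1 rests. The second is any comparison of the two boosters: the same background added to both arms makes them look more alike than they are. Sections 8.7 and 13.3.2 themselves raise increased reactogenicity as a possibility, so a comparison by booster is a natural use of these data. Pre-dose status cannot be reliably recovered afterwards.

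**Working it through.** **1. The plan's own figure.** The only sample size in the protocol is for the primary outcome (10.2): 25% versus 50%, two-sided alpha 0.05, 80% power, 58 per group. The pooled-variance formula without continuity correction gives n = 58 and power 80.2% at that n, so it reproduces. The documents give no expected rate, power or test for reactogenicity.

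**2. Model.** Let v be the proportion with a vaccine-caused symptom. Let b be the proportion who would report the item anyway and whose report passes the filters in 8.3 and 8.7. Take b as independent of v and equal in the two arms, as 1:1 randomisation and blinding imply in expectation.

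- Observed rate: p = 1 − (1−b)(1−v).
- Overstatement of one vaccine's rate: p − v = b(1−v).
- Observed difference: p₂ − p₁ = (1−b)(v₂ − v₁).

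If v₁ = v₂, the observed difference is zero for every b, so type I error is not inflated.

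**3. Inputs for the illustration.** From 10.2: N = 300, up to 10% loss, 1:1 allocation. This gives 300 × 0.9 / 2 = 135 per booster, pooled over the two initial-vaccine strata. Assumed, because the documents give nothing: v = 30% versus 45%, and b from 5% to 40%.

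**4. Power formula.** Power = Φ[(d − 1.96·SE₀)/SE₁], where SE₀ uses the pooled proportion and SE₁ the separate ones.

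Worked line, b = 20%:
- p₁ = 1 − 0.8 × 0.70 = 0.44; p₂ = 1 − 0.8 × 0.55 = 0.56; d = 0.12.
- SE₀ = √(0.5 × 0.5 × 2/135) = 0.06086.
- SE₁ = √((0.44 × 0.56 + 0.56 × 0.44)/135) = 0.06042.
- Power = Φ[(0.12 − 0.11928)/0.06042] = Φ(0.012) = 50.5%.

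With a pre-dose record, those free of the item before the dose can be analysed. The rates are then 30% versus 45% with 135(1−b) per booster. At b = 20% that is 108 per booster and power 62.6%.

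| b | Observed rates | Difference (points) | Power, no pre-dose record | n per booster free of the item | Power, with record (best case) |
|---|---|---|---|---|---|
| 0 | 30.0% vs 45.0% | 15.0 | 72.3% | 135 | 72.3% |
| 5% | 33.5% vs 47.8% | 14.3 | 66.6% | 128.3 | 70.1% |
| 10% | 37.0% vs 50.5% | 13.5 | 61.0% | 121.5 | 67.7% |
| 20% | 44.0% vs 56.0% | 12.0 | 50.5% | 108 | 62.6% |
| 30% | 51.0% vs 61.5% | 10.5 | 41.2% | 94.5 | 56.8% |
| 40% | 58.0% vs 67.0% | 9.0 | 33.2% | 81 | 50.5% |

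**5. Can the existing filters do the work?**
- Rule (a) in 8.3 needs a baseline note of the symptom. None is scheduled.
- Rule (b) needs no record, but it could also remove genuine fatigue or headache after vaccination, and sites may apply it differently.
- Attribution by the participant or coordinator has no pre-dose reference.
- Section 8.7 notes that side effects after the first two doses were recorded for pilot participants. That is not a pre-booster baseline and covers only some participants.

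**The case against.** **The protocol does filter background.** A reader might infer that every fever, headache or bout of fatigue after the dose is counted as reactogenicity. The documents do not support that: 8.7 asks about vaccine-linked symptoms, 8.3 excludes pre-existing and common events, and 8.2.1 adds an investigator's causality assessment. Muscle and joint pain are already restricted, and the injection-site items have little background. This stands. The defect is that the filtering is unanchored, not that it is absent.

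**No test is being weakened.** Objective 4 does not ask for a difference between groups, whereas objective 5 does, and 10.5 names no test for adverse events. For the tolerability hypothesis in 10.1, over-counting is conservative. This also stands: the power figures describe what a comparison could show, not a loss in a prespecified test. Overstated absolute rates are still wrong rates, and dilution is the direction that hides a difference between boosters.

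**The absent placebo arm.** A reader might infer that it undermines the booster comparison, or that background tilts the comparison toward one vaccine. Neither follows. Allocation is randomised 1:1, and participants and assessors are blinded through adverse event reporting at 30 days. A placebo would bear only on the absolute rates, and 4.1 gives an ethical reason for omitting it.

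**Limits of the remedy.** Intermittent symptoms that start by chance after the dose, or later in the same dialysis session, would still count as new. The with-record column is therefore a best case. At b = 5% the gain is only 3.5 points (70.1 − 66.6).

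**What cannot be seen.** The questionnaire is not in the documents and may already ask for change from usual. Table 1 also marks a baseline study assessment at the booster visit, whose content beyond 7.4 is not stated.

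**Conclusion.** The point holds in a limited form. No pre-dose record of the solicited symptoms is scheduled, and six of the eight systemic items have no onset-or-worsening rule. Background that passes the filters overstates each vaccine's rate by b(1−v) and shrinks a booster difference to (1−b) of its true size.

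The algebra holds for any rates under independent and equal background. The amounts do not come from the documents. On the assumed 30% versus 45%, the loss of power against b = 0 runs from 5.7 points at b = 5% (72.3 − 66.6) to 39.1 points at b = 40% (72.3 − 33.2). A pre-dose record recovers at best 3.5 to 17.3 of those points (50.5 − 33.2 at the upper end). If the existing filters work well, b is small and so is the effect.

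This is a cheap improvement to a secondary safety outcome, of modest priority. The primary outcome is untouched.

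**What to change.** 1. In Table 1 and Appendix A, add the same symptom checklist at the booster visit, completed before the injection.
2. In 8.7, define every systemic item as new or worse than the pre-dose record, not only muscle and joint pain.
3. In 8.3, state that the exclusion of commonly occurring events does not remove solicited questionnaire items.
4. In 10.5, say that new-or-worsened rates will be reported by booster, and show alongside them the rates among participants free of the item before the dose.

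Cost: a few minutes and one form page per participant, at a visit that already takes place, plus short text changes in three sections. No extra visit, blood sample or participant is needed. Symptoms that begin by chance after the dose will still be counted, and the report should say so.

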3.2 Secondary Objectives/Outcomes

1. Measurement of Anti-Spike, Anti-NP antibodies, and SARS-CoV-2 specific neutralization at 1 month (30 days) following third dose of vaccine.
2. Determine the effect of a third dose of COVID-19 vaccine on humoral immune response in hemodialysis patients who did not attain convalescent serum levels or exhibiting declining antibody levels below convalescent serum levels of Anti-RBD through measurement of Anti-Spike, Anti-RBD, and Anti-NP antibodies at 3 months, 6 months and 12 months following booster dosage.
3. In a subset of participants, assess cellular immunity through flow cytometry on PBMC and single-cell RNA sequencing prior to, one month, and 6 months following vaccine booster.
4. Evaluate adverse events related to third dose of vaccine through a questionnaire within 48 hours to 14 days and 30 days following third vaccine dose.
5. Differences in COVID-19 infections, symptomatic COVID-19 infections, hospitalization, and death between study groups.

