Prior to receiving a third vaccine dose, quantitative SARS-CoV-2 IgG antibody levels against the full-length spike protein S1 domain, and Receptor Binding Domain (RBD) to assess humoral response will be measured and Anti-SARS-CoV-2 nucleocapsid protein to measure evidence of prior COVID-19 infection. In addition, we will isolate peripheral blood mononuclear cells in a subset to evaluate cellular immune response, however this will only be performed at University Health Network and Sunnybrook Health Sciences Centre as only these centres have the capacity for processing these samples. A neutralization antibody assay developed by the [name] lab will also be used to assess for viral neutralization prior to booster dose at 1 month (30 days) post third dose of vaccine.

[figure not shown]

Figure 2: Four study groups in the BOOST KIDNEY study. Study participants will be randomized 1:1 after stratification by initial vaccine type.

Following the intervention, SARS-CoV-2 antibodies will be measured 1 month, 3 months, 6 months and 12 months post booster vaccination. Neutralizing antibodies will be measured at baseline and 1 month post third dose of booster vaccine. Cellular immunity in a subset will be evaluated at baseline, 1 month and 6 months post third dose of booster vaccine. Adverse events related to third dose of vaccination will be surveyed in the 14 day period following third dose of vaccine, and again 1 month following third dose. The study protocol may be altered if booster doses become available that are intended to target new SARS-CoV-2 variants. Furthermore, the study design will be adaptive, as if patients do not respond to a third dose of vaccine the study protocol may be amended to consider other vaccine booster interventions. All study practices will follow social distancing measures currently recommended by Public Health authorities.

5 PARTICIPANT SELECTION and WITHDRAWAL

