7 STUDY SCHEDULE AND PROCEDURES

7.1 Study Procedure

Participants who meet study eligibility criteria and consent to participate will be enrolled in the study. At study enrolment baseline, serum will be collected for SARS-CoV-2 serology, neutralizing antibodies and in a subset determined by the Investigator, PBMC will be collected for assessment of cellular immunity at Sunnybrook Health Sciences Centre or University Health Network prior to receiving the booster dose. Patients who are already participating in the study “Determining the Safety and Efficacy of COVID-19 Vaccination in the Chronic Kidney Disease Population” (CTO Protocol Number 3604) and have been found to have poor humoral response to COVID-19 vaccination will be prioritized for recruitment. However, if a booster dose of COVID-19 vaccine is approved for subsets of the study population or the study population at large during the study period, patients remain eligible for randomization without serological confirmation of low antibody titres.

Vaccine will be administered by an individual trained in vaccine administration at the site.

Following vaccination, participants will be asked about adverse symptoms related to COVID-19 vaccination through a questionnaire at 48 hours -14 days either in person in the dialysis unit or by telephone and at 1 month post third dose.

Following the intervention with either third dose of booster vaccine, the participant will have blood collection for Anti-SARS-CoV-2 IgG antibodies targeting the full length spike protein, RBD, nucleocapsid protein at 1 month, 3 months, 6 months, and 12 months following receipt of the booster dose. For feasibility, neutralizing antibodies will only be performed at 1 month following third dose. Non-dialysis participants may have bloodwork testing as part of routine

clinical care at each time point to determine if the booster vaccine dose has impacted kidney function including a serum creatinine and a spot urine micro-albumin creatinine ratio.

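### The first adverse-event questionnaire may be given on any day from 2 to 14 with no stated look-back, so its symptom rates depend partly on when participants are asked

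*Combined protocol and SAP*

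**What the plan says.** Secondary objective 4 (section 3.2) is to "Evaluate adverse events related to third dose of vaccine through a questionnaire within 48 hours to 14 days and 30 days following third vaccine dose". Section 8.7 repeats the timing: "Local and systemic AE will be evaluated within 48 hours to 14 days and 1 month post third dose". Section 7.1 describes a "questionnaire at 48 hours -14 days either in person in the dialysis unit or by telephone", followed by another at 1 month. Section 4.1 is looser still: "Adverse events related to third dose of vaccination will be surveyed in the 14 day period following third dose of vaccine". The Protocol Summary, Table 1 and Appendix A carry the same window as a single entry with no day attached.

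Other relevant provisions:
- Section 8.5 collects adverse events from the dose until 30 days after it, and section 8.3 asks about them at every contact.
- Section 8.9.1 sets visit windows for blood samples only.
- Section 11.2 makes questionnaire answers source data, entered straight onto the case report form with no earlier record behind them.
- Sections 10.5 to 10.5.3 describe no analysis of solicited symptoms.
- On onset, section 8.7 cites a heterologous prime-boost study in which "most adverse events occurred within 48 hours of vaccination". It gives no percentage.

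**The concern.** A percentage taken from the first questionnaire would pool participants observed for 2 days with participants observed for 14. It would also pool fresh recall with old recall. Part of the reported rate would then reflect call scheduling rather than the vaccine.

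Tolerability is a stated aim. It is secondary objective 4, and the hypothesis in section 10.1 includes acceptable tolerability. Section 2.3 raises the possibility of greater reactogenicity with heterologous schedules. The safety board is to review these questionnaires at 30 days (section 10.3.1). Because the form is the only source, a common interval may not be recoverable afterwards unless onset day was asked.

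**Working it through.** The documents give no expected symptom rate, power or sample size for tolerability, so there is no plan figure to reproduce.

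**Coverage, from the text.** The first contact falls between day 2 (48 hours) and day 14, so covered time varies by a factor of 14 / 2 = 7. Recall varies in the opposite direction. A reaction that began by 48 hours is at least 14 − 2 = 12 days old at a day-14 call. For someone asked on day 2, the remaining days are asked about only at about day 30, unless another contact intervenes.

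**Size at the extremes.** Let R be the true proportion with a symptom by day 14 and p the share of those whose symptom starts by 48 hours. Both are assumptions. With perfect recall, a day-2 call records R × p and a day-14 call records R, so the shortfall is R × (1 − p).

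| R | p | Recorded at day 2 | Recorded at day 14 | Shortfall (points) |
|---|---|---|---|---|
| 50% | 0.60 | 30% | 50% | 20 |
| 50% | 0.75 | 37.5% | 50% | 12.5 |
| 50% | 0.90 | 45% | 50% | 5 |
| 60% | 0.55 | 33% | 60% | 27 |
| 60% | 0.75 | 45% | 60% | 15 |
| 60% | 0.95 | 57% | 60% | 3 |

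Over R = 20% to 80% and p = 0.55 to 0.95, the shortfall runs from 0.20 × 0.05 = 1 point to 0.80 × 0.45 = 36 points. These figures compare everyone asked at one end of the window with everyone asked at the other. They ignore the 1-month report.

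**A mixed window.** Spread later onsets evenly over days 2 to 14. The rate recorded at day d is then R × [p + (1 − p)(d − 2)/12]. With calls uniform over the window, the mean day is 8. For R = 60% and p = 0.75 this gives 0.60 × (0.75 + 0.25 × 6/12) = 52.5%, against a true 60%.

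**Arm comparison.** If call timing does not depend on arm, both arms share the same expected recorded rate under the null. A simulation of 4,000 trials with 150 per arm, R = 60%, p = 0.75 and uniform timing gave a mean difference of about −0.0004, that is, zero. If the arms truly differ but share the same p, the recorded difference shrinks by the same factor as the rates. For example, true rates of 50% and 60% with p = 0.75, all asked on day 2, are recorded as 37.5% and 45%, a difference of 7.5 points instead of 10.

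**The case against.** The strongest reply is that total follow-up is the same for everyone. The 1-month questionnaire, the 30-day collection in section 8.5 and the questioning at each contact in section 8.3 together cover about 30 days. Objective 4 names both questionnaires, and no section makes the first-questionnaire rate an endpoint on its own. A cumulative 0-to-30-day rate would fit the text. This stands: a reader might infer that a participant's whole symptom record spans only 2 to 14 days, and the documents do not support that. What remains is that no rule combines the two reports, and that the common period relies on month-old recall of brief symptoms in people asked early.

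The form itself is not in the documents. Section 8.7 says its questions are adapted from a provincial adverse-event report, which could carry onset dates or a reference period. That also stands. The gap shown is in the protocol text, not necessarily in the form.

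A reader might also infer that timing is confounded with dialysis modality, since in-centre patients can be asked in the unit and others by telephone. Section 7.1 ties the setting to how contact is made, not to the day. A unit visit or a call can fall anywhere in the window. No modality effect can be claimed or sized from these documents.

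Finally, if most reactions start within 48 hours, an early call still catches most onsets. This is fair, and it is why the shortfall may be small. The same fact makes late calls the ones with old recall.

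**Conclusion.** The point holds for the first questionnaire: its coverage ranges from 2 to 14 days, with no look-back, onset-day or combining rule stated in the protocol. The consequence is imprecise absolute tolerability rates and some blurring of the booster comparison. With an assumed 50% 14-day rate and 60% to 90% of onsets by 48 hours, a day-2 call records 30% to 45%. The true size is unknown because neither quantity is in the documents.

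A reader might go further and suspect that one vaccine is favoured. Allocation is randomised (section 5.5.1), and section 5.5.2 blinds participants, the research team and outcome assessors, with participants unblinded only once adverse-event reporting is complete. Timing therefore has no stated route to differ by arm, and the null comparison is not biased. The primary outcome and sample size are untouched. This is a worthwhile, low-cost improvement to a secondary objective.

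**What to change.** 1. Record the date of each questionnaire and the onset day of every solicited symptom on both questionnaires.
2. Define one fixed interval for everyone, for example injection to the end of day 7, as the tolerability outcome that is reported and compared between boosters. State this in section 8.7 and in the analysis plan under section 10.5.
3. Have the 1-month questionnaire ask about the days since the first contact, so that the interval is complete for all, and state how the two reports are combined.
4. Choose one of two timings. Either place the first questionnaire at or after the end of the interval, or keep early calls and complete the interval at a later contact. The first option lengthens recall of early reactions for participants who would otherwise have been asked sooner. The second keeps early recall fresh, but needs a brief further contact or relies on the 1-month questionnaire for the remaining days.

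The cost is wording in sections 7.1 and 8.7, Table 1 and Appendix A if the timing changes, and an extra field on the form. If the existing form already records onset dates, only the interval and the combining rule need to be written down.
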